8.3. Measures

Sociodemographic and Clinical Characteristics to Describe the Sample

A standardized survey will be used to collect data on participants’ age, race, ethnicity, employment status, level of education, marital status, household income, living situation, gender identity, and clinical comorbidities[34]. We will also collect baseline clinical, disease, and treatment information via chart review such as: Eastern Cooperative Oncology Group (ECOG) performance status, date of initial diagnosis of multiple myeloma, chemotherapy treatment regimen, and date started on maintenance therapy.

Disability

The Late-Life Function and Disability Instrument (LLFDI). The LLFDI is a self-report assessment developed for use in community-dwelling older adults.[35, 36] The function subscale (32 items) measures limitations in specific physical tasks of daily life and the disability subscale (16 items) measures inability to participate in major life tasks. When used with adults with a mean age of 80 years (SEM = 0.4 years), the scores were moderately correlated with a short physical performance battery, gait speed, and lower extremity function.[37] One week test-retest reliability of the function subscale had an intraclass correlation coefficient (ICC) of 0.96. One week test-retest of the disability subscale demonstrated an ICC of 0.68 for frequency scores and 0.82 for limitation scores.

Activity Level

Activity Card Sort modified (ACSm).[38] The Activity Card Sort [39] was developed to measure the instrumental, leisure, and social activity levels of older adults and modified for use with cancer survivors [40]. The ACSm provides a total score and four domain scores: instrumental activities (cooking meals,

PROTOCOL TITLE: *Health Through Activity: A pilot study of a rehabilitation intervention for people living with multiple myeloma*

paying bills, driving), low physical demand leisure (e.g., reading, doing puzzles, using the computer), high physical demand leisure (e.g., golfing, woodworking, gardening), and social activities (e.g., eating at a restaurant, going to parties, going to a place of worship). While originally developed as a manual card sort using labeled, pictorial depictions of the 80 activities, the tool demonstrates adequate reliability without the use of the picture cards [40, 41]. Activity Card Sort scores have been positively associated with quality of life [40, 42], health, and functioning [41].

Individual Activity Targets (IAT): During the first session, the occupational therapist elicits the participant's individual activity goals. The participant rates each activity with Likert scales for three characteristics: frequency of current performance (very often, often, once in a while, almost never, never), importance of the activity (1-10), and satisfaction with the activity (1-10). These ratings were used in the pilot study and provided a simple and pragmatic tool for assessing individualized outcomes

Quality of Life and Cancer-Related Fatigue

Functional Assessment of Chronic Illness Treatment – Fatigue (FACIT-F). The FACIT-F is a 41-item questionnaire consisting of the FACT-G (28 items), which measures health-related quality of life covering four domains of well-being (physical, social/family, emotional, functional), plus 13 fatigue-specific items. The FACIT-F has robust psychometric properties with excellent test-retest reliability (ICC=0.91),[43] validity, and the ability to detect change over time among older adults with cancer.[44-46] A cut off score of 34 is diagnostic of cancer-related fatigue, based on a 0-52 total available score for the fatigue subscale.[47]

Balance, Gait Speed, and Functional Strength

Short Physical Performance Battery.[48] The Short Physical Performance Battery (SPPB) is a multidimensional tool used to assess lower extremity function and is strongly associated with self-reported disability among older adults.[48] The SPPB assesses the ability to stand for ten seconds with the feet in three different positions (i.e., balance), time to walk 3 or 4 meters (i.e., gait speed), and the time it takes to rise from a chair five times (i.e., functional strength).[48] The SPPB is highly recommended as a measure of functional mobility by the EDGE Task Force of the Academy of Oncologic Physical Therapy of the American Physical Therapy Association due to its ease of administration and scoring, excellent test-retest reliability (ICC = 0.81-0.91) and sensitivity to detect change (MCID = 0.5 points).[49, 50] Established normative data and cut-off scores will assist in identifying participants who may be at increased risk of mobility disability.[50, 51] The SPPB produces a composite score, ranging 0-12, with higher scores indicating better function.

PROTOCOL TITLE: *Health Through Activity: A pilot study of a rehabilitation intervention for people living with multiple myeloma*

Aerobic Capacity

2-Minute Walk Test.[52] The 2-Minute Walk Test (2MWT) is a measure of aerobic capacity that assesses walking distance covered in two minutes. Among older adults, the 2MWT has excellent test-retest reliability (ICC=0.95) and established normative data (150.4 meters) and MDC (12.2 meters).[52] The 2MWT correlates highly with the 6-Minute Walk Test ($r = 0.93$) and the Timed Up and Go Test ($r = -0.87$),[52] while there is evidence that the 2MWT is more tolerable than the 6-Minute Walk Test among older adults.[53]

Exercise Self-Efficacy

Self-Efficacy for Exercise (SEE) scale.[54] The SEE scale consists of nine potential exercise barriers and asks the individual to rate their confidence on a 0 (not confident) – 10 (very confident) scale that they could exercise for twenty minutes, three times per week, given each barrier (maximum score of 90 indicates highest exercise self-efficacy). Among older adults, the SEE scale has been shown to have excellent internal consistency (Cronbach's $\alpha= 0.92$) and SEE scale scores significantly predict exercise activity.[54] Although the SEE scale has not been validated in samples of survivors with CRF, a validated measure of ESE in this population does not currently exist, and we feel that the nine barriers appropriately represent scenarios that our participants may regularly encounter.

Acceptability of the intervention

Satisfaction survey. We will use a 7-item survey that we developed for previous studies to assess satisfaction with: the intervention, the therapists, the number and length of sessions, the helpfulness and importance of the intervention content. These items are rated on a 5-point Likert scale with verbal descriptions. The final question asks if the participant would recommend the intervention to another person who was trying to be active while living with multiple myeloma.

Semi-structured interview. [name] will train the project coordinator to conduct the semi-structured interview. During these interviews, the coordinator will solicit feedback on the utility of HTA and recommendations for modifications to the intervention. While the guide serves as a starting point for the conversation, it will evolve to be responsive to the accounts being obtained both from the interviews up to that point and the account emerging in the ongoing interview. We expect the interview to last approximately 20 minutes. With participant permission, the interview will be audiorecorded and transcribed verbatim. Once the transcript has been proofread, the audiorecording will be deleted.

PROTOCOL TITLE: *Health Through Activity: A pilot study of a rehabilitation intervention for people living with multiple myeloma*

We will also conduct one semi-structured interview with each interventionist who delivered the HTA program. The interventionists are valuable stakeholders to provide insight into feasibility and acceptability of this program and to help the study team determine issues related to scalability, implementation, and potential modifications required for future iterations. These semi-structured interviews will be conducted individually by a research coordinator who was not involved in delivery of the intervention to minimize risk of social desirability bias. An interview guide will serve as a starting point for the conversation but will evolve as described above to be responsive to the information being gathered.

Verbal consent will be obtained from each interventionist prior to the interview, including permission to audio-record the interview. Audio-recorded interviews will be transcribed verbatim and the audiorecording will be deleted once the transcript has been proofread.

Data Collection

The table below depicts the schedule and the study staff who will administer the instruments (PC = Project Coordinator, PT = physical therapist, and OT = Occupational therapist). The project coordinator will collect the data by telephone at baseline (Time 1), after completion of the intervention (Time 2) and six weeks after completion of the intervention (Time 3). The occupational and physical therapists will collect data in person during sessions 1 and 6.

Variable	Instrument	# of items	Administered by	Time 1	Session 1	Session 6	Time 2	Time 3
Demographics and Comorbidities	Survey	29	PC	X				
Function and Disability	LLFDI	32 16	PC	X			X	X
Activity level	ACSm IAT	80 variable	PC OT	X	X	X	X	X
Quality of Life and fatigue	FACIT-F	40	PC	X			X	X
Exercise Self-Efficacy	SEE Scale	9	PC	X			X	X
Acceptability	Survey and Interview	7 N/A	PC				X	
Balance, gait, and strength	SPPB	N/A	PT		X	X		
Aerobic Capacity	2MWT	N/A	PT		X	X		

9.0 Data Banking*

No data will be used for anything beyond the analyses described in this protocol.

10.0 Data Management* and Confidentiality

10.1. Analysis.

Aim 1: To evaluate the feasibility of enrolling and retaining participants with multiple myeloma into a pilot test of the refined HTA intervention, delivered from MGH Institute of Health Professions (i.e., within the IMPACT Practice Center or clinical research laboratories) and via telehealth technology.

Aim 2: To evaluate the feasibility of administering the outcome assessment battery that includes patient-reported outcomes of disability, activity level, quality of life, fatigue, and exercise self-efficacy, and performance-based outcomes of balance, gait speed, and strength.

For Aims 1 and 2, we will calculate the following feasibility statistics:

- Screening rate: Number patients screened/ Number patients identified as potentially eligible
- Eligibility rate: Number patients screening positive & eligible / Number screened
- Enrollment rate: Number participants enrolled / Number screened positive & eligible
- Intervention completion rate: There are two metrics for this a) Number participants completing 6 sessions of the HTA intervention/Number of participants enrolled; and b) Number of completed sessions per participant
- Assessment completion rate: Number participants completing each of the three study assessments/Number of participants enrolled

Thresholds for assessing feasibility:

- The screening rate is influenced both by staffing efforts to reach patients and patients' willingness to engage in screening in person or by telephone. Screening rate of at least 75% will indicate feasibility.
- The eligibility rate is influenced by how many people in the clinical population are experiencing disability. Based on our pilot study, we expect this rate to be at least 35%.
- The enrollment rate is one of the most important markers of feasibility as it reflects how many patients experiencing the targeted problem choose to enroll in the study. Enrollment rate of at least 75% will indicate feasibility.
- The intervention completion rate is influenced by the level of burden of the intervention, the health status of the participants, and the perceived benefit of the intervention. In our pilot study, we had a 90% intervention completion rate when using the participants as the unit of analysis (i.e., the first metric listed above). However, in the pilot study, the therapist came to the participant's home to deliver the intervention.

PROTOCOL TITLE: *Health Through Activity: A pilot study of a rehabilitation intervention for people living with multiple myeloma*

For this study, we will consider it feasible if 75% of participants complete all six sessions and if the mean number of sessions is greater than or equal to 4.

- The assessment completion rate is influenced by the burden (time and cognition) involved, the perceived meaningfulness of items, and the flexibility of mode of completion (e.g., by computer, by telephone per preference). In our pilot we had a 80-90% assessment completion rate depending on study arm. For this study, an assessment completion rate of 85% will indicate feasibility.

Aim 3: To assess the acceptability of the refined HTA intervention and assessment battery and utilize stakeholder feedback to identify further modifications to enhance acceptability.

For Aim 3, we will calculate descriptive statistics on the satisfaction survey data. We will also explore the interview data. All interviews will be audio-recorded and professionally transcribed. Immediately following the interview, the coordinator will listen to the recording and take detailed field notes that will describe the content and context of the interview, ending with a summary of stakeholder opinions and recommendations. Field notes will also provide details about the evolution of the interview guide and questions and themes that seem important as the interviews unfold. Transcripts, field notes, and interventionist field notes will be imported into NVivo for qualitative analysis.

Drs. [name] and [name] will independently read the transcripts and field notes. Informed by the tradition of Miles and Huberman, we will code the data, then discuss and compare our codes to create a formal codebook with operational definitions. Coding is an iterative process that involves labeling segments of data. Some codes will reflect concepts introduced by participants, and many will reflect my own areas of interest such as difficulties with the intervention, or positive experiences within the intervention. We will then look within and across coded texts to extract converging themes and reach consensus on principal themes. We will use the themes to modify the manual in consultation with the full research team.

Thresholds for assessing acceptability: In terms of the satisfaction survey, any item that generates a mean score of < 4 will trigger consideration of making a modification to the treatment manual or study procedures. We will explore the interview data to help us understand what may be driving the lower satisfaction rating and brainstorm potential modifications that could be adopted in response. Independent of the survey scores, we will also use the interview data to identify potential changes. The decision to modify the protocol for subsequent studies will be informed by both the number of people expressing the opinion and the salience or potency of the concern e.g., a recommendation to add an education topic to the patient education manual or a

PROTOCOL TITLE: *Health Through Activity: A pilot study of a rehabilitation intervention for people living with multiple myeloma*

misunderstanding by even one participant could lead us to edit the study materials or procedure.

- 10.2. **Sample Size Determination.** Consistent with the intent of a feasibility study [55, 56], this exploratory analysis is primarily intended to develop the intervention and evaluate the feasibility and acceptability of the refined HTA program and is **not powered to test effectiveness hypotheses**. Based upon our previous studies in developing and testing behavioral interventions [57-59], we expect that 20 participants will be feasible to recruit within a 12-month period and will give us rich data to determine the feasibility and acceptability of the intervention.
- 10.3. **Data Storage.** All participant information and study source documents will remain confidential and be accessible only to study staff. Paper copies will be kept in locked file cabinets of locked offices belonging to [name]. Electronic files will be stored on secure institutional computers using MGH Dropbox. All study data will be maintained in the MGH version of REDCap. REDCap is a free, secure, HIPAA-compliant web-based application hosted by the MGB Research Computing, Enterprise Research Infrastructure & Services (ERIS) group.
- 10.4. **Data Security.** Participant data will be collected using MGH REDCap. All participants will be assigned an id number and only one password-protected file will link the name with the study id. Participants' responses to survey questions will remain confidential. Study staff undergo training on study procedures as well as data management to ensure data security and patient confidentiality (e.g., good practice of locking computers before stepping away from desk, not using names where outside team members could hear).

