Early observations of our study indicate that attending in-person study visits may be a barrier for some participants. A few eligible participants have expressed a desire to participate but have chosen not to enroll due to difficulty attending in-person study visits. Furthermore, due to the immunocompromised condition of our participants, each of the three enrolled participants have had to cancel/reschedule in-person study visits because of illness, resulting in interrupted study participation. We anticipate that this is a barrier we may regularly encounter in this population. Enrolled participants and those choosing not to enroll have voiced that telehealth study visits would be appealing. Finally, our experience delivering the revised HTA intervention to the initial study participants has revealed the potential feasibility of delivering the intervention via telehealth (except for Study Visits 1 and 6 which include physical therapy tests/examination, necessitating in-person study visits). We feel that providing participants with a telehealth option may enhance study enrollment and retention without compromising the integrity of the intervention. This would potentially improve scalability/implementation of the intervention should it prove to be efficacious. As such, we will explore the feasibility of providing an option for participants to receive the revised HTA intervention via telehealth technology

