prescription” (i.e., goal and action plan) is collaboratively generated to allow the participant to complete the activity and exercise program in the coming week. The action plan is practiced with the therapist present whenever feasible and the individualized exercises are first demonstrated by the therapist with return demonstration by the participant.

The HTA Treatment Manual describes the theoretical base of the intervention and the structure of the six sessions. The six sessions ideally occur once a week (rescheduled as needed for participant convenience) and last 50 to 75 minutes. Sessions will be individually delivered. Sessions 1 and 6 will occur in-person at MGH IHP either in the IMPACT Practice Center or in the clinical research laboratories. Participants will be given the option of completing study visits 2-5 in-person at MGH IHP or virtually via telehealth technology.

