21.0 Local Number of Subjects

- 21.1. We expect to enroll at least 4 and up to 20 participants into this study.
- 21.2. We do not expect any screen failures in this study. Eligibility can be determined prior to enrollment by screening the medical record and asking self-report questions.

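### Does the redundant mean-sessions threshold in the intervention-completion rule need to be changed?

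*Combined protocol and SAP*

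**What the plan says.** Section 10.1 defines two completion metrics. The first is "Number participants completing 6 sessions of the HTA intervention/Number of participants enrolled". The second is "Number of completed sessions per participant", with no denominator spelled out. The thresholds later in the section join the two: delivery is judged "feasible if 75% of participants complete all six sessions and if the mean number of sessions is greater than or equal to 4".

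Three other statements set the context:
- The programme has a maximum of six sessions: "The six sessions ideally occur once a week (rescheduled as needed for participant convenience) and last 50 to 75 minutes" (section 8.2).
- The possible sample size is given in section 21.1: "We expect to enroll at least 4 and up to 20 participants into this study".
- The only completion benchmark is from the team's pilot, where "we had a 90% intervention completion rate when using the participants as the unit of analysis". Section 10.1 itself notes that the pilot was delivered in participants' homes.

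Neither cut-off is derived from a calculation, and the plan does not say how the two conditions relate to each other.

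**The concern.** A rule with two thresholds joined by *and* reads as two hurdles. Here the second lies below a level that the first already guarantees, so it looks like an arithmetic oversight in a criterion attached to a primary endpoint (section 7.1 lists completed intervention visits among the feasibility measures).

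What would be at stake is how results are read:
- In a passing result, a statement that both thresholds were met would suggest corroboration that the mean cannot supply.
- In a failing result, the mean could still clear 4 and be presented as partial success.

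A mixed result is not far-fetched. The pilot's setting differed, and section 2.0 reports that "each of the three enrolled participants have had to cancel/reschedule in-person study visits because of illness".

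**Working it through.** The plan gives no derived figure to reproduce, so the check is whether the mean condition can ever decide the outcome.

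**Inputs.** Maximum sessions per person: 6 (section 8.2). Completion cut-off: 75% of those enrolled; mean cut-off: 4 (section 10.1). Sample size n: 4 to 20 (section 21.1).

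**Lower bound.** If a share p attends all six sessions and everyone else attends none, the mean is 6p, the lowest value possible for that p. At p = 0.75 this is 4.5. A mean of 4 is already guaranteed at p = 4/6 = 66.7%, below the 75% cut-off.

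**Whole-number check.** The smallest passing count is ceil(0.75n), and the lowest mean compatible with it is 6 x ceil(0.75n)/n:

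| n | Completers needed | Lowest mean |
|---|---|---|
| 4 | 3 | 4.50 |
| 7 | 6 | 5.14 |
| 10 | 8 | 4.80 |
| 15 | 12 | 4.80 |
| 20 | 15 | 4.50 |

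Over n = 4 to 20 the minimum is 4.5 (at n = 4, 8, 12, 16 and 20) and the maximum is 5.14 (at n = 7).

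**Enumeration.** For each n, take every number of completers and every session total among non-completers (0 to 5 sessions each). This gives 7,871 outcomes.
- 75% part met, mean part missed: 0.
- Mean part met, 75% part missed: 3,110. All are not feasible under the rule as written.
- Verdict with the mean condition deleted: identical in all 7,871.

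**The borderline at n = 20.** With k completers the mean lies between 6k/20 and (6k + 5(20 - k))/20.
- k = 14: 84/20 = 4.2 to 114/20 = 5.7. The mean part is always met; the verdict is not feasible.
- k = 15: 90/20 = 4.5 to 115/20 = 5.75. Both parts are met; the verdict is feasible.

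**Denominator of the mean.** If the mean were taken only over those who started, non-starters with zero sessions would drop out and the mean could only rise. The condition could bind only if completion were taken over starters and the mean over all enrolled, with more than 1 - 4/4.5 = 11.1% never starting. An example is 20 enrolled, 17 starters and 13 completers: 13/17 = 76.5%, while the lowest mean is 78/20 = 3.9. That reading contradicts the denominator section 10.1 gives for completion.

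**How often would the two parts disagree?** True completion and dropout pattern must be assumed, because the documents give neither for this study. At n = 20 with constant attrition per session (continuation probability equal to completion to the power 1/6), the chance of fewer than 15 completers together with a mean of at least 4 is:

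| True completion | 60% | 65% | 70% | 75% | 80% | 85% | 90% |
|---|---|---|---|---|---|---|---|
| Chance | 74% | 69% | 56% | 38% | 19% | 7% | 1% |

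At 60%, 65% and 70% completion the chance is 12%, 17% and 19% if non-completers attend no sessions, and 87%, 75% and 58% if they attend five. These are chances of an outcome that the rule classifies correctly; none is an error rate.

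**The case for a change.** The strongest case for a change is that it would be cheap and safe. One sentence could say that the 75% criterion decides and that sessions per participant are descriptive. Since no verdict can move, making the edit after enrolment has begun would not shift the goalposts. It would also remove in advance any temptation to lean on a mean that has been met when the completion criterion has failed. If true completion is somewhat below 75%, such a split result is likely under several dropout patterns.

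The arithmetic in that case stands, and so does the observation that a met mean confirms nothing once 75% have completed. The need for an edit does not:
- The wording already rules out a partial-success verdict, because both conditions must hold. With 14 of 20 completing, the answer is not feasible whatever the mean.
- Authors who stressed the mean against that rule would be at fault in reporting. Relabelling the statistic would not stop them, because it would still be reported.
- The likelihood of a split result depends on assumptions the documents do not supply. At the pilot's 90% completion it is about 1%, although the pilot's home delivery means that 90% may not carry over.
- Deleting a prespecified criterion part-way through a study makes the plan look less demanding and invites questions, with nothing gained in return.

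**Conclusion.** The mean-sessions condition is redundant, and no change to the plan follows, because there is no gain. Meeting the 75% criterion forces a mean of at least 4.5, so the 75% criterion alone decides, and the verdict is the same with or without the mean condition in every possible outcome for 4 to 20 participants. This rests on completion being taken over everyone enrolled, as section 10.1 states, and on a maximum of six sessions. It needs no assumption about dropout.

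Having a participant-level rate alongside an amount-delivered measure is ordinary in a feasibility study, and the mean describes something the 75% rate does not. Analysts can report sessions per participant descriptively and remark that the 75% criterion settles the question, leaving the prespecified criteria as they are.

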7.0 Study Endpoints

- 7.1. Primary study endpoints are the *feasibility* of recruitment and data collection activities. *Feasibility* of enrolling and retaining participants with multiple myeloma into a pilot test of the refined HTA intervention delivered from MGH IHP and via telehealth will be measured by the following rates: # screened, # found eligible, # enrolled, # intervention visits completed, and # surveys completed.
- 7.2. Secondary study endpoint is the *acceptability* of the Health Through Activity program. *Acceptability* of the Health Through Activity program will be assessed utilizing semi-structured interviews to solicit feedback on the utility of HTA and recommendations for modifications to the intervention.

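### Aim 3 promises to assess acceptability of the assessment battery, but no described survey topic, interview purpose, endpoint or threshold addresses the battery

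*Combined protocol and SAP*

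**What the plan says.** Aim 3 appears in section 1.0 and again in section 10.1, where it reads "To assess the acceptability of the refined HTA intervention and assessment battery", followed by the use of stakeholder feedback to identify changes.

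The parts of the plan that carry out this aim are:

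- **Endpoint 7.2.** Acceptability of the Health Through Activity (HTA) program "will be assessed utilizing semi-structured interviews to solicit feedback on the utility of HTA and recommendations for modifications to the intervention".
- **Satisfaction survey (8.3).** Seven items, rated on 5 points, "to assess satisfaction with: the intervention, the therapists, the number and length of sessions, the helpfulness and importance of the intervention content". The last item stays with the program: "The final question asks if the participant would recommend the intervention to another person".
- **Participant interview (8.3).** In it "the coordinator will solicit feedback on the utility of HTA and recommendations for modifications to the intervention". The guide is not fixed: "While the guide serves as a starting point for the conversation, it will evolve to be responsive to the accounts being obtained".
- **Interventionist interview (8.3).** One per therapist, on this ground: "The interventionists are valuable stakeholders to provide insight into feasibility and acceptability of this program".
- **Schedule table (8.3).** The survey and interview are marked at Time 2 only. Time 3 follows six weeks after the end of the intervention.
- **Acceptability threshold (10.1).** A survey item with a mean below 4 prompts the team to consider changing the manual or the study procedures. Interview data can also prompt changes, whatever the survey scores.
- **Assessment completion (10.1).** A rate of 85% is set as a criterion of feasibility under Aims 1 and 2.

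**The concern.** A stated aim should have at least one planned observation behind it. Here the aim has two objects, and every instrument described for it concerns only one of them. If the study is run exactly as written, nobody is asked by design whether the questionnaires and performance tests were too long, too tiring or beside the point. The report on Aim 3 would then either be silent on the battery or rest on whatever a few participants, out of at most 20, happened to volunteer.

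This matters because the study is meant to prepare for efficacy trials, and the battery is a likely candidate for use in them. Completion shows who finished. It does not show whether those who finished found the load reasonable or the questions relevant, and section 20.5 ties gift cards of $25, $50 and $25 to completing the assessments.

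**Working it through.** No sample size, power or error-rate figure bears on this point, and the plan states no figure to reproduce. The check compares the aim with each component that serves it, then makes a simple count.

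**Step 1: match the aim to its components.**

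| Component | Section | Covers the intervention? | Names the battery? |
|---|---|---|---|
| Aim 3 | 1.0, 10.1 | yes | yes |
| Acceptability endpoint | 7.2 | yes | no |
| Satisfaction survey topics | 8.3 | yes | no |
| Participant interview purpose | 8.3 | yes | no |
| Interventionist interview purpose | 8.3 | yes | no |
| Examples of the team's own codes | 10.1 | yes | no |
| Item-mean threshold | 10.1 | yes, through the survey items | no item to act on |

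**Step 2: count the survey topics.** The description yields: the intervention, the therapists, number of sessions, length of sessions, helpfulness of content, importance of content, and willingness to recommend. That makes 7, which agrees with the stated number of items if each topic is one item. Topics on the battery: 0 of 7. Interview purposes that name the battery: 0 of 2.

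**Step 3: see whether another measure fills the gap.** The nearest is the assessment completion rate. Section 10.1 says that burden and how meaningful the items seem both influence it, so it carries some indirect information. The plan uses it to judge feasibility, however, and it cannot separate a well-accepted battery from one completed despite its burden.

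**Step 4: context on burden.** From the schedule table, the coordinator-administered outcome instruments are the Late-Life Function and Disability Instrument (32 + 16 = 48 items), the modified Activity Card Sort (80), the FACIT-F (40) and the Self-Efficacy for Exercise scale (9):

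48 + 80 + 40 + 9 = 177 items at each of three time points.

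The text of 8.3 gives the FACIT-F 41 items (28 + 13), which makes 178. The individual activity ratings, the Short Physical Performance Battery and the 2-Minute Walk Test come on top, at sessions 1 and 6. These counts show why burden is worth asking about. They do not measure the gap.

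**The case against.** The strongest reply is that the plan is not blind to the battery. The interview guide may evolve, and some codes are to come from concepts that participants raise. Section 10.1 lets interview data lead to changes in study materials or procedures even when only one person raises a problem. Completion has a threshold, and section 11.0 has the team review missing participant-reported outcomes weekly. Section 15.0 plans to seek further community input on assessments before later studies. The survey and interview guides are not in the documents, so the survey count rests on a prose description. All of this stands, and it limits how far the point can go.

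A reader might draw three stronger conclusions that the documents do not support.

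- **That the battery half of Aim 3 cannot be answered at all, or that a poor battery would go into the next trial with no signal.** The open interviews, the completion and missing-data figures and the planned community input all leave some route for a signal. The accurate statement is that there is no planned measure or threshold.
- **That asking at Time 2 is itself a flaw.** By then the performance tests and activity ratings have been scheduled twice, and the questionnaires have been met at least once (twice if the Time 2 battery comes first). Time 3 only repeats known instruments. The timing of the interventionist interviews is not stated, so nothing can be said about their order.
- **That the total item load sizes the defect.** Adding the 29 baseline survey items gives 29 + 3 × 177 = 560, but those 29 are demographics and comorbidities, not outcome measures. An item count is in any case not evidence about acceptability.

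What the reply does not supply is a planned question. Volunteered remarks are not a measure of a stated aim, and input sought before later studies does not assess acceptability in this one.

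**Conclusion.** The point holds as a mismatch between aim and measurement. Aim 3 names the assessment battery, while 0 of 7 described survey topics, 0 of 2 stated interview purposes, the acceptability endpoint and the item-level threshold address it. Half of one stated aim has no planned measure, and what evidence there is would be incidental or indirect. The primary feasibility endpoints are unaffected and no safety question arises. It should be corrected because it is a gap in the design of a stated aim, beyond missing detail, and the repair is small.

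This rests on two assumptions: that the description in 8.3 fairly represents the seven survey items, and that the interview guides hold no fixed question on the assessments that the protocol leaves unmentioned. If either instrument already has such a question, it is enough to state it in 8.3 and 7.2.

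**What to change.** Measure what the aim promises:

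1. Add one or two 5-point items to the existing Time 2 satisfaction survey, one on the burden and one on the relevance of the questionnaires and performance tests. Give them after the Time 2 battery, so that participants have just completed it.
2. Add one fixed prompt on the assessments to the participant guide and one to the interventionist guide. Keep these prompts even as the guides evolve.
3. Apply the existing rule (item mean below 4) to the new items.
4. Name the battery in endpoint 7.2.

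Repeating the items at Time 3 is optional. If the team does not want to collect this information, the alternative is to remove the battery from Aim 3 in sections 1.0 and 10.1, so that the aim matches 7.2.

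The first route costs a minute or two per participant and a minor instrument amendment. The second costs only a wording change, but gives up direct feedback on the battery in this study.
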